9.3.2.2 Secondary outcomes and further endpoints

Secondary outcomes

- Time to First Moderate or Severe COPD Exacerbation
 - Time to First Moderate COPD Exacerbation
 - Time to First Severe COPD Exacerbation
- Number of Moderate or Severe COPD Exacerbations
 - Number of Moderate COPD Exacerbations
 - Number of Severe COPD Exacerbations

Further endpoints:

- All-Cause Inpatient Mortality
- Number of Unique Pulmonary Medications
- Number of Hospitalizations for a Respiratory Condition
- Major Cardiovascular Adverse Events (MACE)
- Home oxygen therapy (HOT)

Moderate exacerbations will be defined as an outpatient visit with a diagnosis code for COPD in any field + a prescription for an oral corticosteroid or an antibiotic for respiratory infections,. Severe

exacerbations will be defined as a hospitalization with a primary diagnosis for COPD. (**Chatterjee 2012**)

Unique pulmonary medications will be defined as the following treatments: LAMA, LABA, SAMA, SABA, inhaled/oral glucocorticoids, systemic glucocorticoids, antileukotriene agents, biologics (anti-IgE, anti-IL-5, anti-IL-4), allergy medications, xanthines (theophylline), and mycolytics.

Major Cardiovascular Adverse Event (MACE) will be defined as ischemic stroke, myocardial infarction (MI), or inpatient death. Stroke will be defined as absence of a doubt flag and a disease claim for ICD-10 I60.x - Subarachnoid haemorrhage, I61.x - Intracerebral haemorrhage, I63.x - Cerebral infarction, or I67.8 - Other specified cerebrovascular diseases, a measure previously validated based on ICD-9 code equivalents to have a PPV between 85 and 98% [**Andrade 2012; Tirschwell 2002; Roumie 2008**]. MI will be defined as absence of a doubt flag and a disease claim for ICD-10 I21.x - Acute myocardial infarction or I22 - Subsequent myocardial, a measure previously validated based on ICD-9 code equivalents to have a PPV of 94% using US Medicare claims [Kiyota 2004] and 88.4% PPV using US commercial claims [Wahl 2010]. Inpatient death will be defined as either absence of a doubt flag and a disease claim or Discharge Summary Data with a death-related diagnosis (ICD-10 O96.x - Death from any obstetric cause; O97.x - Death from sequelae of obstetric causes; I46.1 - Sudden cardiac death, so described; R96 - Other sudden death, cause unknown; R98 - Unattended death; R99 - Other ill-defined and unspecified causes of mortality) or the occurrence of Discharge Summary Data with either Destination After Discharge as 8 - Completed (Death and so on.) or Discharge Summary Data with Outcome at the Time of Discharge is Death.

Home oxygen therapy (HOT) will be defined according to presence of the following:

- Health claim codes that include home/domiciliary oxygen therapy:

- 114041610 - Add-on fee of materials for domiciliary oxygen therapy (others)
- 114042770 - Oxygen therapy add-on fee (home-care patient home visit fee (1) 1)
- 114043670 - Oxygen therapy add-on fee (home-care patient home visit fee (2) a)
- 114045470 - Remote monitoring add-on fee (home oxygen therapy guidance management fee [others])
- 114004910 - Installation type liquid oxygen reservoir add-on fee
- 114005010 - Portable type liquid oxygen reservoir add-on fee
- 114006110 - Oxygen tank add-on fee (others)
- 114006210 - Oxygen enricher add-on fee
- 114006310 - Oxygen tank add-on fee (portable oxygen tank)
- 739210000 - Liquid oxygen/portable liquid oxygen container (LGC)
- 739220000 - Oxygen cylinder/large size
- 739230000 - Oxygen cylinder/small size
- 739250000 - Liquid oxygen/portable liquid oxygen container (LGC) (remote islands and other)
- 739260000 - Oxygen cylinder/large size (remote islands and other)
- 739270000 - Oxygen cylinder/small size (remote islands and other)

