8. RESEARCH QUESTION AND OBJECTIVES

To compare the early intervention effectiveness of Tio/Olo vs. Tio among COPD patients.

The primary objective of this study is to:

- Compare time to LAMA/LABA/ICS triple therapy initiation among initiators of Tio/Olo vs. initiators of Tio.

The secondary objectives of the study are to compare the following among initiators of Tio/Olo vs. initiators of Tio:

Secondary outcomes

- Time to First Moderate or Severe COPD Exacerbation
 - Time to First Moderate COPD Exacerbation
 - Time to First Severe COPD Exacerbation
- Number of Moderate or Severe COPD Exacerbations
 - Number of Moderate COPD Exacerbations
 - Number of Severe COPD Exacerbations

Further endpoints:

- All-Cause Mortality,
- Number of Unique Pulmonary Medication Prescriptions
- Number of Hospitalizations for a Respiratory Condition
- Major Cardiovascular Adverse Events (MACE)
- Home oxygen therapy (HOT)

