9.2 SETTING

9.2.1 Definitions

Study Period: the entire period of time that includes the baseline period, the cohort entry date (index date), and follow-up period for the study population. The study period will be from **01 April 2015** (180 days prior to Spiolto approval date of 28 September 2015 in Japan) to **31 March 2019** (end of available data).

Patient Selection Period: the period of time for which patients are eligible to enter the cohort. The earliest date of the patient selection period is **28 September 2015**, (the Spiolto approval date in Japan). The latest date of the patient selection period is 31 December 2018, corresponding to 90 days before the end of available data (31 March 2019), ensuring that all patients have at least 60 days after the cohort entry date to identify a second prescription for index therapy and at least 30 days to be capable of the 30-day overlap to determine the triple therapy initiation outcome.

Cohort Entry Date: Date of entry to the initial cohort of Tio/Olo vs. Tio users (*first prescription*).

Baseline Period: the 180-day period that ends 1 day prior to the cohort entry date used to assess covariate information. The earliest start of the baseline period would be 01 April 2015, corresponding to 180 days prior to the approval date of Spiolto.

[figure not shown]
Follow-Up Period: the period starting at the second prescription for Tio/Olo or Tio within 60 days of the cohort entry date (first prescription) and ending at the earliest occurrence of the outcome (use of triple therapy), or the first occurrence of inpatient death, disenrollment, or end of the study period (31-Mar-2019). A sensitivity analysis will employ an as-treated censoring approach to further censor upon discontinuation of index therapy or initiation of the other index treatment arm. Patients may have different lengths of follow-up (i.e. variable follow-up).

Since health care is nationalized in Japan, the notion of enrollment is not applicable. Therefore, a proxy enrolment criterion defined as start of enrolment = date of first inpatient/outpatient encounter; end of enrolment = date of last inpatient/outpatient encounter will be used. “Enrolment” herein will refer to this proxy enrolment measure. For entry into the study population, patients will be required to have had at least 180 days of enrollment prior to the cohort entry date.

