9.12 BIAS

In principle, electronic pharmacy dispensing records are considered accurate because pharmacists fill prescriptions with little room for interpretation, and are reimbursed by insurers based on detailed, complete, and accurate claims submitted electronically (Levy 2003; Sternbach 1988). Pharmacy dispensing information is usually seen as the gold standard of drug exposure information compared to self-reported information or prescribing records in medical records.

The population-based nature of the database will avoid selection bias and ensure external validity. Confounding bias through observable covariates will be controlled for by the design, which includes propensity score matching. Specifically, compared to traditional propensity

score matching, high dimensional propensity scores will be used to reduce overfitting while retaining baseline covariate balance in matched groups (**Schneeweiss 2009**).

To minimize misclassification of the recorded patient characteristics, previously validated algorithms or code lists will be used whenever available. Code lists will be reviewed by the qualified medical reviewers prior to implementation. Basic plausibility checks will be implemented for continuous variables (e.g. age, etc.).

The covariates chosen in [section 9.3.3](#) are hypothesized to be confounders in the relationship between exposure and outcome. The range and quantity of variables selected are aimed to make the two exposure groups more comparable so that the effect estimates may more readily have a causal interpretation.

COPD patients who start on Spiriva® Respimat® may be different than Spiolto® Respimat® initiators in the clinical course and severity of COPD. Use of propensity score matching aim to reduce bias due to confounding. The addition of covariates chosen by hDPS will further aid in reducing bias by empirically selecting for strong confounders. However, it is possible that inclusion of some variables may introduce rather than remove bias (i.e. as collider bias or M-bias). Nevertheless, such biases are demonstrated to be minor, and inclusion of variables preceding exposure are generally thought to improve rather than degrade validity (**Rassen 2011**).

The requirement of second fill for inclusion in the study could lead to immortal time bias. However, as the follow-up will begin after the second fill rather than at the cohort entry date, this requirement is unlikely to bias the findings.

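### Two further endpoints need a text correction before programming: MACE names ischemic stroke but its codes include haemorrhage, and the pulmonary-medication count states neither its unit nor how the index drug is handled

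*Combined protocol and SAP*

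**What the plan says.** **MACE.** Section 9.3.2.2 gives the composite as: "Major Cardiovascular Adverse Event (MACE) will be defined as ischemic stroke, myocardial infarction (MI), or inpatient death". The next sentence supplies the codes: "Stroke will be defined as absence of a doubt flag and a disease claim for ICD-10 I60.x - Subarachnoid haemorrhage, I61.x - Intracerebral haemorrhage". It continues with I63.x (cerebral infarction) and I67.8 (other specified cerebrovascular diseases). The whole list is then described as "a measure previously validated based on ICD-9 code equivalents to have a PPV between 85 and 98" per cent. On code lists in general, section 9.12 says: "Code lists will be reviewed by the qualified medical reviewers prior to implementation".

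**Pulmonary-medication count.** The definition in section 9.3.2.2 opens: "Unique pulmonary medications will be defined as the following treatments: LAMA, LABA, SAMA, SABA, inhaled/oral glucocorticoids, systemic glucocorticoids, antileukotriene agents", and goes on to biologics, allergy drugs, xanthines and mucolytics. It says nothing about the index drug. The same section names the endpoint "Number of Unique Pulmonary Medications", while the abstract and section 8 name it "Number of Unique Pulmonary Medication Prescriptions". Section 9.2.1 defines follow-up as "the period starting at the second prescription for Tio/Olo or Tio within 60 days of the cohort entry date", so every patient has an index prescription on the first day of follow-up. Section 9.2.1 also ends follow-up at the outcome, which it identifies as triple therapy. It does not say whether that end date applies to this count.

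**The concern.** In the MACE definition, two adjacent sentences disagree. The component is called ischemic, but its codes take in subarachnoid and intracerebral haemorrhage. A programmer can run the list without difficulty, so the mismatch could pass unnoticed into a table that reports haemorrhages as ischemic stroke.

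The medication count has a different fault: it is under-specified. If the unit is the drug class, the exposure is part of the outcome. Tio/Olo patients start one class higher than Tio patients before anyone adds a drug, and a higher count in that arm need not mean more added treatment. If the unit is the product, the arms start level. The plan does not say which unit applies, and its two names for the endpoint point in different directions. This should be settled before results are seen, because the choice can change the size and direction of a between-arm comparison.

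Section 9.7.3 repeats the further endpoints in the as-treated analysis, so both definitions feed two sets of results.

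**Working it through.** **MACE: name against content**

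| Code group | Label in section 9.3.2.2 | Fits the name ischemic stroke? |
|---|---|---|
| I60.x | Subarachnoid haemorrhage | No |
| I61.x | Intracerebral haemorrhage | No |
| I63.x | Cerebral infarction | Yes |
| I67.8 | Other specified cerebrovascular diseases | Not specific |

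Two of four code groups contradict the name, one matches it, and one is not specific to ischemia. No other section says which was intended. The PPV is attached to all four groups together, so it cannot be carried over to a shortened list. The number of events involved cannot be calculated, because the documents give no event counts by code. In addition, a patient with a haemorrhage who dies in hospital stays in the composite through the death component, whichever list is used.

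**Medication count: what the index drug contributes**

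Inputs: section 7 describes Tio/Olo as a LABA plus a LAMA, and Tio as a LAMA. Section 9.3.2.2 lists both classes. Section 9.2.1 starts follow-up on an index prescription.

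Built-in difference = (units from the index drug in Tio/Olo) − (units from the index drug in Tio).

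| Counting rule | Tio/Olo | Tio | Difference |
|---|---|---|---|
| Distinct classes, index drug counted | 2 | 1 | 2 − 1 = +1 |
| Distinct products, index drug counted | 1 | 1 | 1 − 1 = 0 |
| Index product and refills excluded | 0 | 0 | 0 − 0 = 0 |

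Now let a Tio patient add one LABA product, and compare with a Tio/Olo patient who adds nothing. Both then receive a LAMA and a LABA.

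| Counting rule | Tio/Olo | Tio + LABA | Difference |
|---|---|---|---|
| Distinct classes, index drug counted | 2 | 1 + 1 = 2 | 0 |
| Distinct products, index drug counted | 1 | 1 + 1 = 2 | −1 |
| New classes only, index product excluded | 0 | 1 | −1 |

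The first rule measures total treatment and builds the exposure in. The last measures added treatment and records the step up. The product rule lies between: the arms start level, but identical therapy scores differently according to how it is packaged. If prescriptions were counted literally, as the name in section 8 could suggest, refills might enter as well, and no fixed difference can be stated.

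**Overlap within the list.** One entry covers inhaled and oral glucocorticoids and the next covers systemic glucocorticoids. Oral steroids fall under both, so one drug could score twice.

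**The case against.** On MACE, the strongest reply is that this is a one-word slip. The adjective appears in a single sentence, the code list is explicit, the PPV supports that list, section 9.12 promises medical review of code lists, and section 9.8 lets definitions change by documented amendment. Much of this stands: the list is usable, and review may catch the mismatch. But neither provision says which side is right.

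On the count, the reply is that the plan never says that classes are counted or that the index drug is included, and that the name in the abstract and section 8 favours prescriptions or products. This also stands. A reader might infer from the class-like list that the endpoint is certainly biased towards a higher count for Tio/Olo. The documents do not support that. The +1 holds only if classes are counted, and by product the built-in difference is 0.

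A reader might also be tempted to combine the 6% and 10% one-year triple-therapy rates in section 9.5 into an expected gap in the count. That is not supported either. Those rates are planning assumptions, follow-up length varies, and section 9.2.1 ends follow-up at triple therapy. If that rule governs this count, the escalating prescription falls on the end date and may not be counted at all.

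The glucocorticoid overlap is minor. The systemic entry may have been meant for injected steroids, since section 9.3.3 has a covariate for oral or injected corticosteroids, and no between-arm effect is shown.

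**Conclusion.** The MACE point holds without conditions: the name and the codes disagree, with two of four stroke code groups labelled haemorrhage. It does not follow that the endpoint cannot be run, that the codes rather than the name are the error, or that the MACE comparison would shift by a material amount. The documents settle none of these.

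The medication-count point holds as missing specification. The unit, the handling of the index drug and the end of the counting window are not stated. The built-in difference is +1 by class and 0 by product. This rests only on the listed classes, the composition of the two index drugs and the start of follow-up.

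Both are further endpoints. The primary analysis and study size are unaffected. The corrections are worth making before programming because they cost little and remove a choice that would otherwise be made during analysis.

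**What to change.** **MACE.** Make the name and codes agree, in one of two ways:
- Rename the component stroke (ischemic or haemorrhagic). The codes and the cited PPV stay. The cost is one text edit.
- If ischemic stroke is intended, remove I60.x and I61.x, justify keeping I67.8, and stop citing the 85 to 98% PPV for the shortened list. The cost is possibly fewer events and no validation figure for that list.

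**Pulmonary-medication count.**
- Count distinct drug classes newly prescribed after the start of follow-up, and exclude the index product and its refills in both arms. A LABA added in a Tio patient then still counts.
- State whether counting stops at triple-therapy initiation.
- Use one endpoint name in the abstract, section 8 and section 9.3.2.2.
- Make the two glucocorticoid entries non-overlapping.

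The price is one of interpretation. The count would measure added treatment, not total treatment burden, and Tio/Olo patients have no LABA step left to add. The report should say so when the arms are compared. All of this is text and code-list editing before programming, and no new model is needed.

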9.2.2 Study population

The study cohort will include all patients who initiate Tiotropium/Olodaterol (Tio/Olo) or Tiotropium (Tio) during the patient selection period. Initiation (new use) will be determined based on no prescription claims for Tio/Olo or Tio during the baseline period or during all available data prior to cohort entry date. All patients will additionally be required to have a second claim for the index medication within 60 days after cohort entry to ensure primary adherence of index therapy.

The following exclusion criteria will then be applied to generate the unmatched cohort:

- Aged <40 years on cohort entry.

[figure not shown]
Proprietary confidential information © 2020 Boehringer Ingelheim International GmbH or one or more of its affiliated companies

- Any LAMA, LABA, ICS maintenance therapy (alone or in combination) during the 180-day baseline period prior to cohort entry for maintenance treatment and not cough, i.e. duration >30 days, or any prescription within the 30 days prior to cohort entry.
- Patients without continuous enrolment (days since first inpatient/outpatient encounter in the data) during the baseline period.
- No prior diagnosis of COPD [ICD-10: J41*, J43*, J44* and doubt (UTAGAIFLG) = 0 (no)]
- Patients without a second prescription claim of their index medication within 60 days after the cohort entry date.
- Diagnosis of asthma [ICD-10: J45* and doubt (UTAGAIFLG) = 0 (no)] during the baseline period.
- Diagnosis of lung cancer [ICD-10: C34*, D02.2, Z80.1, Z85.1 and doubt (UTALAIFLG) = 0 (no)] or lung transplant (Health claim code: 150317670, 150322510, 150322610, 150336510, 150336610, 150336710, 150399270) prior to the cohort entry date using all available data.
- Patients who initiate both Tio/Olo and Tio simultaneously on the cohort entry date.
- Any use of triple therapy (LAMA + LABA + ICS) during the baseline period or between the cohort entry date and 1 day prior to the start of follow-up.

All patients will be selected into the first treatment arm (Tio/Olo or Tio) that they qualify for and will not be allowed to re-enter the cohort by design.

The cohort will then be used to construct two matched cohorts (not mutually exclusive) according to the: 1) basic propensity scores and 2) high dimensional propensity scores

Figure 2 Depicts the flow diagram of patients.

Basic Propensity Score Matching

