9.3.2 Outcomes

9.3.2.1 Primary outcomes

Triple Therapy Use

[figure not shown]
The primary outcome of interest is incident rate of triple therapy initiation (first event per patient) defined as any LAMA/LABA/ICS fixed dose combination or any concurrent use for 30 consecutive days of the following:

- any LAMA/LABA fixed dose combination + any ICS single formulation
- any LAMA single formulation + any LABA/ICS fixed dose combination
- any LAMA single formulation + any LABA single formulation + any ICS single formulation

MDV data has limited information on treatment duration with the days of prescription recorded as 1 day for most patients. Therefore, a days supply of 30 days will be assumed. Although we will require at least 30 days of overlap, the first date of triple therapy overlap will serve as the outcome event date, as corresponds to the initiation of triple therapy. Looking into the future to satisfy the requirement of overlap for at least 30 days has the potential to inflict immortal person-time, but is necessary to differentiate concurrent use when subsequent medication is added (see [Figure 3](#) - example Patient A) from an early sequential prescription fill when subsequent medication is switched to (see [Figure 3](#) - example Patient B).

Figure 3

Illustration of outcome

Censoring

Patients will be censored if they had an occurrence of any of the following: outcome (initiation of triple therapy), death, or end of data. The analysis will use an intention-to-treat censoring approach, which does not account for treatment change. A sensitivity analysis will employ an as-treated censoring approach to further censor upon discontinuation of index therapy or initiation of the other index treatment arm. Thus, events will be assigned to exposure groups according to that patient's original index medication, even if that patient discontinued or crossed over.

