9.3.3 Covariates

The covariates listed below consist of demographics, medications, comorbidities, and other variables that are hypothesized to confound the relationship between exposure and outcome. Covariates will be identified based on data recorded within 180 days prior to or on the index date (date of

dispensing/initiation of the exposure), unless otherwise specified. If multiple measurements are made in the baseline period, then the most recent measurement will be used.

There is an additional variable for “doubt diagnosis” related to each disease diagnosis. Only confirmed diagnoses will be used for all disease variables (this represents ~95% of all diagnoses).

Absolute and relative frequencies of each covariate will also be reported. Detailed descriptions of the listed covariates can be found in Annexes 2 and 3. The measure definitions for diagnoses are subject to modification to further incorporate disease codes/names as deemed appropriate upon further exploration of the data during study implementation.

Demographics (last recorded)

- Age
- Sex
- Year of Cohort Entry
- Hospital Size (as a proxy for urban/rural).

Concomitant Medications

- Oral/Injected Corticosteroids
- Short acting beta agonist (SABA) (number of claims)
- Short acting muscarinic antagonist (SAMA) (number of claims)
- Systemic Xanthines
- Systemic Antileukotrienes
- Interleukin Inhibitors for Asthma
- Non-steroidal Respiratory Anti-inflammatories
- Opioids/Narcotics
- Systemic Antihistamines
- Oral Antibiotics for a Respiratory Condition (number of claims)
- Cough and Cold Preparations
- Diabetes Mellitus Medications, excluding Insulin
- Insulin
- Cytostatics
- Antirheumatics, Biologic
- Antirheumatics, Non-Steroidal
- Antithrombotic Agents
- Lipid-lowering Agents
- Antihypertensives/Diuretics
- Antiepileptics/Psycholeptics/Psychoanaleptics
- Antipsoriatics
- Antivirals
- Thyroid Therapies
- Vaccinations

[Antibiotics + Respiratory diagnosis, [REDACTED] can try to find antibiotics specific to respiratory conditions]

Comorbidities/Symptoms

- COPD Exacerbations (number of exacerbations)
- All-Cause Hospitalization
- Hospitalization due to Respiratory Condition
- Acute Myocardial Infarction, AMI
- Angina Pectoris
- Peripheral Vascular Disease, PVD
- Heart Failure, HF

- Hypertension
- Cardiac Arrhythmias
- Cerebrovascular Disease
- Any Cancer (except nonmelanoma skin cancer)
- Allergic Rhinitis
- Chronic Sinusitis
- Bronchiectasis
- Pneumonia
- Chronic Bronchitis

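### The home oxygen endpoint counts continuing claims from patients already on oxygen as outcome events, with no exclusion of prior users and no predefined baseline covariate

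*Combined protocol and SAP*

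**What the plan says.** Home oxygen therapy is one of five further endpoints. Section 9.3.2.2 defines it in one sentence, "Home oxygen therapy (HOT) will be defined according to presence of the following", and then gives 15 codes under the line "Health claim codes that include home/domiciliary oxygen therapy". The definition has no first-use condition, washout period or minimum number of claims.

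Section 9.2.1 says that the follow-up period is used to identify the outcome, and that follow-up starts at the second fill of the index inhaler. The exclusion list in section 9.2.2 does not mention earlier oxygen use. Section 9.3.3 opens with "The covariates listed below consist of demographics, medications, comorbidities, and other variables that are hypothesized to confound", and home oxygen is not in the lists that follow.

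The primary outcome is handled differently. Section 9.2.2 excludes "Any use of triple therapy (LAMA + LABA + ICS) during the baseline period" and extends that exclusion to the day before follow-up starts. Section 9.3.2.1 limits the outcome to the first event per patient. Home oxygen has neither safeguard.

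**The concern.** Home oxygen produces repeated claims. A patient on it at entry will probably have another claim soon after the second inhaler fill, whichever drug was started. Under the plan as written, that claim meets the endpoint. The event says something about disease severity at entry and nothing about the effect of the inhaler.

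Two consequences follow. If prior use is equal in the two arms, the same number of events is added to both and the ratio moves toward 1. If prior use differs, the difference is carried into the outcome and can be read as a treatment effect. Section 9.12 itself accepts that the two groups of initiators may differ in clinical course and severity, so imbalance cannot be ruled out.

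**Working it through.** **Reading the rules together**

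1. Event rule (9.3.2.2): any listed code is sufficient.
2. Window (9.2.1): from the second fill onward. A claim before that is not an event; a continuing claim after it is.
3. Eligibility (9.2.2): earlier oxygen is not an exclusion.
4. Adjustment (9.2.2, 9.3.3): the basic propensity score uses predefined variables only, and home oxygen is not one. The high-dimensional score can draw on inpatient and outpatient health claim codes, so oxygen codes are candidates but are not assured of selection.

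Continuing users therefore enter the cohort and count as events, and only one of the two scores might balance them.

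**Size, on assumed inputs**

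The documents give no rate of new or prior home oxygen, so there is no planned figure to reproduce. Let p be the proportion with prior use and r the 1-year risk of a new start among the rest. If every prior user has a claim in follow-up, the observed risk is p + (1 − p) × r.

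*Illustration A: equal prior use, a true difference.* Assume r = 0.021 on tiotropium/olodaterol and 0.03 on tiotropium, so the true ratio is 0.021 / 0.03 = 0.70. The prior-user share of tiotropium events is p divided by the observed tiotropium risk.

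| p | Tio/Olo risk | Tio risk | Observed ratio | Prior users among Tio events |
|---|---|---|---|---|
| 1% | 0.01 + 0.99 × 0.021 = 0.0308 | 0.01 + 0.99 × 0.03 = 0.0397 | 0.78 | 25% |
| 3% | 0.03 + 0.97 × 0.021 = 0.0504 | 0.03 + 0.97 × 0.03 = 0.0591 | 0.85 | 51% |
| 5% | 0.05 + 0.95 × 0.021 = 0.0700 | 0.05 + 0.95 × 0.03 = 0.0785 | 0.89 | 64% |
| 10% | 0.10 + 0.90 × 0.021 = 0.1189 | 0.10 + 0.90 × 0.03 = 0.1270 | 0.94 | 79% |

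*Illustration B: loss of power.* Take 1,829 per arm, the count of tiotropium/olodaterol initiators in section 9.5 if all were matched, with assumed new-start risks of 3% and 5% (true ratio 0.60). The test is a two-sided 5% comparison of two proportions, with pooled variance under the null. Power is 87% with no prior use. With p = 2%, 5%, 10% and 15% in both arms, the observed ratio is 0.72, 0.81, 0.88 and 0.91, and power is 71%, 53%, 35% and 26%.

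*Illustration C: unequal prior use, no true difference.* Assume r = 0.04 in both arms, with p = 5% on tiotropium and 8% on tiotropium/olodaterol. The risks are 0.05 + 0.95 × 0.04 = 0.0880 and 0.08 + 0.92 × 0.04 = 0.1168. The ratio is 0.1168 / 0.0880 = 1.33 with no treatment effect. With the imbalance reversed it is 0.0880 / 0.1168 = 0.75.

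**The case against.** **The endpoint is never called new.** A reader might infer that the plan presents existing oxygen as new events. It does not: home oxygen is never described as new, incident or first. The accurate statement is that continuing claims count and cannot be separated from new starts. No model is given for this endpoint either; section 9.7.1.3 covers triple therapy only. For that reason the working uses simple risks and makes no claim about when in follow-up a difference would appear.

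**Adjustment may help.** The high-dimensional score might select oxygen codes. Both scores also include related severity markers: number of exacerbations, respiratory and all-cause hospitalization, pneumonia and heart failure. This stands as mitigation of imbalance. It does not assure balance on oxygen itself, and even perfect balance leaves the dilution in illustrations A and B.

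**Prior oxygen may be rare here.** Recent maintenance therapy and prior triple therapy are excluded, so 5% to 10% may be too high. That is fair and cannot be settled from the documents. Even 1% moves the ratio in illustration A from 0.70 to 0.78.

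**In-hospital oxygen.** A reader might also infer that oxygen given during admissions is counted, making the endpoint partly a repeat of severe exacerbation. The documents do not establish this. The code list is headed as home or domiciliary oxygen, and nothing shows how the codes are billed. What remains is a query: 11 of the 15 labels name no home setting (five of the nine 114-series codes and all six 739-series codes, for example "739220000 - Oxygen cylinder/large size"), no care setting is specified, and the database includes inpatient claims.

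**Low rank.** This is a further endpoint with no stated hypothesis or power. That limits the importance of the point but does not answer it.

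**Conclusion.** The point holds for prior users. Followed as written, the plan counts continuing home oxygen as outcome events. This dilutes the comparison if prior use is balanced and confounds it if not. The rule itself gives this result, so more than a missing detail is at issue.

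The direction follows from the text. The size does not: the assumed new-start risks, the 1% to 15% range of prior use, and a claim in follow-up for every prior user are all outside the documents. On those assumptions a true ratio of 0.70 is observed as 0.78 to 0.94, and a 5% against 8% imbalance alone gives 1.33 or 0.75.

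The documents do not support extending the criticism to the primary or secondary outcome definitions, or treating inpatient capture as shown.

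**What to change.** 1. In section 9.3.2.2, define the endpoint as the first listed claim during follow-up among patients with no listed code in all available data before follow-up starts. Section 9.2.2 already uses an all-data look-back for lung cancer and transplant.
2. Apply this restriction before matching for the home oxygen analysis, or state that broken pairs are accepted.
3. Report baseline home oxygen by arm and preferably add it to the predefined covariates in section 9.3.3, so that both scores use it. This changes the matched cohorts for every endpoint, including the primary, so it should be decided before matching. For the home oxygen analysis itself it adds little once prior users are removed.
4. As a query to the data provider: can the 11 codes whose labels name no home setting arise on inpatient claims? If so, count them only on outpatient claims.

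The cost is a look-back flag built from codes already listed, possibly a second matching run, and fewer patients and events for this endpoint. Because section 9.4 says that records from different hospitals cannot be linked, oxygen billed elsewhere before entry would still be missed; the report should say so.
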